12.2 Sample Size Calculation Process

88 cases
Sample size calculation process Based on preliminary experimental results, sample size was calculated using PASS, with a 20% dropout rate, resulting in a total sample size of 88 cases (22 cases in each group).

Input:

Power and Alpha

Power 0.95

Alpha 0.05

Group 4

Group Allocation Equal

Effect size

Means 30 34 50 53

K 1

σ 761519

Numeric Results
Means: 30 34 50 53

Power	Average	n	G	Total	K	Std Dev of Means	Standard Deviation	Effect Size	Alpha
0.9707	3.00	4		12	1.00	9.91	6.00	1.6515	0.0500
0.9875	4.00	4		16	1.00	9.91	7.00	1.4156	0.0500
0.9526	11.00	4		44	1.00	9.91	15.00	0.6606	0.0500
0.9526	17.00	4		68	1.00	9.91	19.00	0.5215	0.0500

One-Way Analysis of Variance F-Tests

Dropout-Inflated Sample Size (Continued)

Average Group Sample Size n	Group	Dropout Rate	Sample Size	Dropout-Inflated Enrollment Sample Size Ni	Expected Number of Dropouts Di
17.00	1 - 4	20%		17	22
	Total		68	88	5

13. Ethics of Clinical Research

The clinical study will follow the World Medical Association Declaration of Helsinki and other relevant regulations. Before the start of the study, the trial protocol will be implemented only after approval by the ethics committee. Before each subject is enrolled in the study, the investigator is responsible for fully and comprehensively introducing the purpose, procedures, and possible risks of the study to the subject or their agent, and a written informed consent form will be signed. Subjects should be informed that they have the right to withdraw from the study at any time. The informed consent form should be retained as a clinical study document for reference. The privacy and data confidentiality of subjects will be protected during the study.

14. Collection and Storage of Samples/Specimens

None.

15. Study Progress

Not available.

16. References

[2] Neira VM, Kovesi T, Guerra L, Campos M, Barrowman N, Splinter WM. The impact of pneumoperitoneum and Trendelenburg positioning on respiratory system mechanics during

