12.1 Statistical Methods

All data were statistically analyzed using SPSS 26.0 software, with $P<0.05$ indicating a statistically significant difference. Count data were expressed as cases or percentages and analyzed using the Chi-square test or Fisher's exact test. Normality of measurement data was evaluated using the Kolmogorov-Smirnov test or Shapiro-Wilk test. Measurement data conforming to a normal distribution were expressed as mean \pm standard deviation ($x\pm s$) and analyzed using the t-test; count data with repeated measurements were analyzed using one-way ANOVA; skewed or unknown-distribution measurement data were expressed as median (interquartile range) [median (IQR)] and analyzed using the Mann-Whitney U test.

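### The sizing F-test assumes one common SD although the protocol's own inputs are four very different SDs; 88 is conservative, but Welch's ANOVA should be the named four-arm test.

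*Protocol*

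**What the plan says.** Section 12.2 introduces the calculation with "Based on preliminary experimental results, sample size was calculated using PASS". The inputs are alpha 0.05, target power 0.95, four groups, "Group Allocation Equal", "Means 30 34 50 53", and a list of four sigmas. The Sample Size row of the Protocol Summary prints that list legibly as 7, 6, 15, 19. The method is "One-Way Analysis of Variance F-Tests".

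The output has four rows, and each applies a single SD to all four groups: 6, 7, 15, then 19. The SD 19 row (17 per group, effect size 0.5215, power 0.9526) is carried forward "with a 20% dropout rate, resulting in a total sample size of 88 cases (22 cases in each group").

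Section 12.1 tests measurement data for normality. Normally distributed data are summarised by mean and SD "and analyzed using the t-test"; skewed data go to the Mann-Whitney U test. One-way ANOVA appears only for count data with repeated measurements. No unequal-variance method is named.

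**The concern.** There is one sigma per mean, and the input list is unsorted (7 before 6), whereas the output rows are sorted by SD. Since the figures come from a preliminary experiment, the plain reading is that these are the SDs of the four arms. The largest and smallest variances are then 361 and 36, a ratio of about ten. An F-test with one pooled error variance does not describe such data, and no row of the output models the four SDs together.

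Two things follow. The stated power is not the power at the protocol's own inputs. And a test that pools variances need not hold its 5% level when spreads differ this much, particularly if the arms end with different numbers of analysable patients. Section 12.1 does not repair this: it names a two-sample test for a four-arm outcome and does not say which form is meant.

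**Working it through.** **Inputs** (Section 12.2, with the sigmas as printed in the Protocol Summary): means 30, 34, 50, 53; SDs 7, 6, 15, 19; alpha 0.05; equal allocation; 20% dropout.

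**1. The plan's own figure.**
- The mean of the means is 41.75. The squared deviations are 138.06, 60.06, 68.06 and 126.56, which sum to 392.75. SD of means = √(392.75/4) = 9.91, as printed.
- Power = P(F′ > F crit), with F′ noncentral F on 3 and 4(n − 1) df and λ = n × 392.75 / SD².
- For SD 19 and n = 17: λ = 17 × 392.75 / 361 = 18.5, df 3 and 64, power 0.9526.
- The other rows also reproduce: SD 6, n = 3: 0.9707; SD 7, n = 4: 0.9875; SD 15, n = 11: 0.9526.
- Dropout: 17 / 0.80 = 21.25, rounded up to 22; 4 × 22 = 88.

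The arithmetic is right for a common SD of 19.

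**2. Power with one SD per arm.** The average variance is (49 + 36 + 225 + 361)/4 = 167.75, so the root-mean-square SD is 12.95 and f = 9.91/12.95 = 0.765. The noncentral F with that SD gives 0.9998 at 17 per arm. Simulation with the four SDs in place gives about 0.9997 for the F-test and 0.9998 for Welch's ANOVA. About 9 per arm already gives 0.95 (F 0.956, Welch 0.953).

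**3. False-positive rate** (normal data, equal means, SDs 7/6/15/19, at least 200,000 simulated trials per setting):

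| Arm sizes | F-test | Welch's ANOVA |
|---|---|---|
| 17/17/17/17 | 0.071 | 0.051 |
| 22/22/22/22 | 0.071 | 0.050 |
| 22/22/22/17 | about 0.09 | about 0.05 |
| 12/17/22/22 | 0.042 | about 0.05 |

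The last two rows only illustrate direction. The reason for it shows in the expected mean squares: within arms, Σ(nᵢ − 1)σᵢ²/(N − 4); between arms under equal means, Σ(1 − nᵢ/N)σᵢ²/3.
- Equal arms: both are 167.75. The F ratio is centred correctly, and the excess comes from its heavier tail.
- 22/22/22/17 (N = 83): within = (21 × 310 + 16 × 361)/79 = 155.5; between = (61/83 × 310 + 66/83 × 361)/3 = 171.6. The error term is too small.
- 12/17/22/22 (N = 73): within = (11 × 49 + 16 × 36 + 21 × 586)/69 = 194.5; between = (61/73 × 49 + 56/73 × 36 + 51/73 × 586)/3 = 159.3. The error term is too large.

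**4. The test that Section 12.1 names.** For the two-sample t-test in its equal-variance form, with equal arms of 17 or 22, the rate over all six SD pairs is 0.049 to 0.056. At 22 (SD 7 or 6) v 17 (SD 19) it is about 0.08. For SD 7 v 19, the pooled variance averages (21 × 49 + 16 × 361)/37 = 183.9. The test therefore works with 183.9 × (1/22 + 1/17) = 19.2, while the true variance of the difference is 49/22 + 361/17 = 23.5.

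**The case against.** - **The F-test is not the stated primary analysis.** This stands. Section 12.1 reserves one-way ANOVA for repeated count data. A reader might infer that the primary comparison runs at 7%; the protocol does not support that, because the 7% belongs to the sizing test. The named t-test is close to 5% with equal arms.
- **The power discrepancy is in the safe direction.** This stands. A reader might take the mismatch to mean that the trial is underpowered; the opposite holds at these inputs.
- **The 7% needs a particular null.** This stands as a limit. It arises when means are equal and spreads are not. If FiO₂ had no effect on the whole distribution, the arms would share one SD and the F-test would keep 5%. The planning spread is broadly wider where the mean is larger, and the preliminary experiment is of unstated size, so the tenfold variance ratio is itself uncertain.
- **Unequal arms are speculative.** This stands in part. The plan is equal allocation with the same 20% dropout in each arm, and nothing supports severe one-sided attrition. But Sections 4.2, 5.4 and 6.1 describe a post-randomisation exclusion for Group A only, so some imbalance is foreseeable. Its direction is not: the protocol does not tie the SDs to groups A to D.
- **Pairwise comparisons with a pooled ANOVA error would mislead.** A reader might add this, but the protocol names no such procedure.
- **Variance checks belong in an SAP.** This is fair for diagnostics, and none is faulted here. But Section 12.1 does fix the test, and Section 12.2 does fix a model that its own inputs contradict.

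**Conclusion.** The concern holds in a limited form. The common-SD model in Section 12.2 does not match the inputs printed beside it, if the four sigmas are arm SDs, which is the natural reading but not a stated one. The figure 0.9526 is correct for SD 19 in every arm and understates the power at the four SDs (about 0.9997), so there is no case for changing 88.

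The cost is in error control: about 7% instead of 5% for the sizing F-test with equal arms, and about 8% for the named t-test in the least favourable pairs at 22 v 17, in its equal-variance form. Both figures assume normal data, equal means and the planning SDs. The inflation is modest. The case for acting is that a method that holds 5% in every setting examined is available at almost no cost, and that naming it would also bring the four-arm sizing and the two-sample analysis into line.

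**What to change.** In Section 12.1, for normally distributed four-arm outcomes including the primary outcome, name Welch's ANOVA with Games-Howell pairwise comparisons in place of the t-test.

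In Section 12.2, state that 0.9526 at 17 per group assumes SD 19 in every group, say whether 7, 6, 15 and 19 are the arm SDs, and if so add the power at those SDs (about 0.9997 at 17 per group). Leave the sample size at 88.

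The cost is a few sentences. SPSS 26, the software named in Section 12.1, offers both procedures in one menu. No extra patients are needed. At the planning SDs no power is lost; if every arm did have SD 19, Welch's ANOVA would have power 0.945 against 0.953 for the F-test at 17 per arm, and 0.986 against 0.988 at 22.
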